1 Diabetic Neuropathy: Function-Structure of Corneal Nerves to Assess Injury - Repair

2

3 Running title: corneal sensitivity and diabetic neuropathy

4

5

6

7 The study is catalogued NCT04222660.

8

9

10 Study Protocol

11 The purpose of this study is to test a new approach for the early detection of DPN.
12 Diabetes patients meeting the criteria were recruited from the Diabetes Clinics and non-diabetic
13 subjects from the general veteran population. A written and informed consent was obtained
14 from all participants. The study adhered to the Declaration of Helsinki and was approved by the
15 Institutional Review Board (#201610799). Participants were divided into two groups: diabetic
16 with peripheral neuropathy and non-diabetic with no history of peripheral neuropathy.

17 Inclusion Criteria: 1) Type 2 diabetes diagnosed based on the opinion of an Endocrinologist,
18 the absence of a history of ketoacidosis, and a C-peptide > 0.8 ng/ml. 2) At least 10 year known
19 duration of diabetes. 3) Age ≥ 50 yr. 4) HbA1c $< 9.0\%$. 5) Mild to moderate PN based on
20 response to Michigan Neuropathy Screening Instrument (MNSI),¹⁸ nerve conduction and
21 amplitude determined using DPNCheck, medical record, presence or absence of ankle reflex,
22 vibration threshold and 10g monofilament sensation. Exclusion Criteria: 1) History of neurologic,
23 muscular, genetic, or other condition known to affect muscle function or exercise tolerance. 2)
24 Electrolyte abnormalities, untreated hypothyroidism, abnormalities in calcium, phosphate, or
25 magnesium concentrations, or any other metabolic disturbance affecting neural function. 3)
26 Cigarette smoking in the past year. 4) Peripheral vascular, cardiac, pulmonary, or any other
27 disorder affecting blood or tissue oxygenation. 5) Use of any medication known to alter
28 peripheral nerve function. 6) History of diabetic foot ulcer. 7) History of corneal disease including
29 dry eye. 8) History of wearing contacts. 9) Any other medical or psychological condition judged
30 to limit compliance with the protocol or interpretation of results.

31 The study included 28 patients with type 2 diabetes and peripheral neuropathy (24 male
32 and 4 female). The average age of the diabetes patients was 66.8 ± 1.9 , with duration of
33 diabetes 20.0 ± 2.6 and hemoglobin A_{1C} 8.2 ± 0.3 . The non-diabetic subjects (11 male and 5
34 female) were younger 49.8 ± 5.0 .

35 **Clinical neuropathy assessment:** The MNSI questionnaire was self-administered.
36 Each applicant was encouraged to answer yes or no to each of the 15 questions. A score of ≥ 4
37 was considered abnormal. During the MNSI examination a health professional examined the
38 feet, for deformities, dry skin, calluses, infections, and ulcers. Quantitative sensory testing
39 included the presence or absence of ankle reflexes and vibration and monofilament sensation at
40 the dorsum of the great toe.¹⁹ Nerve conduction values were determined using a point of care
41 device *DPNCheck* (*DPNCheck*, NeuroMetrix, Inc., Waltham, MA). Manufacture instructions
42 were followed, briefly after skin preparation, the probes were coated with the conductive gel and
43 applied directly to the skin, posterior to the lateral malleolus.²⁰ Up to four recordings were made
44 as individual tolerance allowed. The recordings were averaged.

45 **Ophthalmic assessment:** All patients underwent a visual acuity assessment. Provided
46 answers to two questionnaires the Ocular Surface Disease Index (OSDI) and Dry Eye
47 Questionnaire (DEQ-5). To evaluate cornea sensitivity each patient underwent a Cochet-
48 Bonnet aesthesiometer examination and blinking response determination following application
49 of a drop of isotonic saline (308 mosmol/liter) or Muro-128 solution 5% sodium chloride (1710
50 mosmol/liter) (Rugby Laboratories, Livonia, MI). This study was performed by having the
51 subject rest their chin comfortably on a support. Three CMOS cameras (Imaging Development
52 Systems GmbH, Obersulm, Germany), one positioned in front of the subject and two positioned
53 laterally, were used to observe both eyes simultaneously. Custom software was used to
54 synchronize video streams and obtain images (MATLAB R2012a, The MathWorks Inc., Natick,
55 MA). Video was taken continuously at 30fps of each subject as an isotonic solution was
56 delivered to the left eye. The response was video recorded for 60 sec after a 10 sec delay.
57 After a 15 min wash and rest period the procedure was repeated using a drop of Muro-128
58 solution 5% sodium chloride. An image collector was used offline to retrieve video frames every
59 10 seconds from each eye drop concentration epoch; therefore 15 images were analyzed
60 subject per solution. Fiji image analysis software was used by a masked technician to measure

61 the visible surface area of both eyes between the upper and lower eyelids. In each recording
62 epoch, the ratio of time the eyelids were closed are presented as a percentage of the subjects'
63 maximum visible eye surface area between the eyelids during that epoch.

64 **Data Analysis**

65 Results are presented as mean \pm S.E.M. Comparisons between the control and diabetic
66 subjects were conducted using Student t-test (Prism software; GraphPad, San Diego, CA). A p
67 value of less than 0.05 was considered significant.

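### The stated purpose is early detection of DPN, but the two groups and the unadjusted t-test can support only a cross-sectional mean difference between diabetic patients with neuropathy and younger non-diabetic subjects.

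*Combined protocol and SAP*

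**What the plan says.** The Study Protocol section gives one purpose: "The purpose of this study is to test a new approach for the early detection of DPN". It then defines two groups, diabetic "with peripheral neuropathy and non-diabetic with no history of peripheral neuropathy".

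Under Inclusion Criteria, patients need type 2 diabetes with a minimum known duration ("2) At least 10 year known" duration) and neuropathy at entry ("5) Mild to moderate PN based on" the MNSI, DPNCheck conduction and amplitude, the medical record, ankle reflex, vibration threshold and monofilament). The participant summary confirms this: "The study included 28 patients with type 2 diabetes and peripheral neuropathy (24 male" and 4 female), with a mean diabetes duration of 20.0. The 16 non-diabetic subjects (11 male, 5 female) are reported as younger: "female) were younger 49.8 ± 5.0", against 66.8 ± 1.9 for the patients.

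Ophthalmic assessment describes a Cochet-Bonnet examination and a blink recording after isotonic saline, repeated with 5% sodium chloride after a 15-minute rest. No later visit is described.

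Data Analysis consists of mean ± S.E.M., a Student t-test for "Comparisons between the control and diabetic" subjects, and a threshold of p<0.05.

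**The concern.** To show that a test detects neuropathy early, a study needs people in whom neuropathy is absent, subclinical or not yet recognised, and some way of showing that the test finds it sooner or better than existing methods. Here every case had already been identified as having PN, using the existing methods and the medical record.

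Nor can the comparison isolate neuropathy. Every participant with PN has diabetes and every participant without a history of PN does not. Age runs in the same direction, and the test makes no adjustment for it.

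What is at stake is the conclusion. A significant t-test reported under the stated purpose could be read as evidence that corneal measures detect DPN early, or that the difference is caused by neuropathy. The design supports neither reading.

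**Working it through.** The documents give no power, effect size or accuracy figure, so there is no stated number to reproduce. The main check compares the purpose with the design.

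**1. What the purpose needs and what is present**

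| Needed | Present in the documents |
|---|---|
| Participants at an early or unrecognised stage | None; PN is an entry criterion for all 28 cases |
| A diabetic group without PN | None; all 16 comparators are non-diabetic |
| Follow-up to later onset | None described |
| Accuracy analysis (cut-off, sensitivity, specificity, AUC) | None; t-test only |
| Comparison with existing tests on timing or accuracy | None; existing tests were used to select the cases |
| Adjustment for age | None |

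Counts agree: 24 + 4 = 28 cases and 11 + 5 = 16 comparators. In the cross-table of diabetes by PN, two of the four cells are empty (diabetes without PN; PN without diabetes). No reanalysis of the group contrast can separate the two factors.

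**2. Age**

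The mean difference is 66.8 − 49.8 = 17.0 years. Assuming normal ages, the AUC for age alone is Φ(17.0/√(SD₁² + SD₂²)).
- If ± is the S.E.M., as Data Analysis says results are presented: the SDs are 1.9 × √28 = 10.1 and 5.0 × √16 = 20.0, and the AUC is 0.776.
- If ± is the SD: the SDs are 1.9 and 5.0, and the AUC is 0.999.

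On either reading, age alone separates the groups better than a corneal measure that only just reaches p<0.05 (step 3).

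**3. What p<0.05 would mean for individuals**

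Assumptions: equal-variance normal outcomes (the blink outcome is a bounded percentage, so this is approximate), a two-sided test (sidedness is not stated) and complete data (completeness is not stated).
- Smallest significant standardised difference: d = t(0.975, 42) × √(1/28 + 1/16) = 2.018 × 0.3134 = 0.632.
- AUC = Φ(0.632/√2) = 0.673.
- Sensitivity at 90% specificity = Φ(0.632 − 1.282) = 0.258.

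Varying the assumptions changes little:

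| Assumption | d | AUC | Sensitivity at 90% specificity |
|---|---|---|---|
| Two-sided, 28 vs 16 | 0.632 | 0.673 | 26% |
| One-sided, 28 vs 16 | 0.527 | 0.645 | 23% |
| Two-sided, about 80% with data (22 vs 13) | 0.712 | 0.693 | 28% |

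These figures describe separation of these two groups. No figure for early detection can be computed.

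**The case against.** The strongest reply is that the purpose is one general sentence. It speaks of testing an approach; it does not say that this study demonstrates early detection, estimates accuracy or isolates neuropathy. Comparing clearly affected with unaffected subjects is a usual first step for a new test. That is fair, and a reader should not infer that the documents claim to have shown early detection. What remains is that nothing in the text limits the purpose to that first step.

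The documents may also be an extract: the first reference number in the text is 18, so a qualification of the aim could stand elsewhere. That cannot be settled here. The point concerns the protocol and SAP as provided.

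Mild to moderate disease might be called early. But mild severity is not early detection: the patients had already been identified, and no mild-only or severity analysis is described. Conversely, a reader might infer that all cases had advanced or well-established neuropathy. The documents do not say so. Criterion 5 is a composite with no rule for how many findings must be abnormal, so some patients may be normal on individual tests.

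A reader might take the label in Data Analysis ("Comparisons between the control and diabetic" subjects) as evidence that the contrast was redefined by diabetes status. It is better read as shorthand for the groups defined in Study Protocol.

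The age imbalance is disclosed, and it is a matter of control selection as much as of purpose. It belongs here only because it further limits what a difference can be attributed to.

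**Conclusion.** The point holds. The design lacks the property its stated purpose requires, and the purpose should be narrowed. A significant result would support only this: corneal measures differ on average between patients with long-standing type 2 diabetes and mild to moderate PN, and younger non-diabetic subjects with no history of PN. It would not show early detection, and it would not separate neuropathy from diabetes or age. This conclusion is structural and rests on no numerical assumption.

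The figures give scale only. Under the normality, two-sidedness and completeness assumptions above, significance is reached at d = 0.63 (AUC about 0.67; 26% sensitivity at 90% specificity), so p<0.05 does not by itself show useful separation of individuals.

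Two stronger readings are not supported. One is that age explains any difference found: the documents give no relation between age and the corneal measures, so the size of an age effect cannot be calculated. The other is that the study has no value: the cross-sectional comparison remains usable if it is described as such.

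**What to change.** Recruitment is complete, so the remedy is to the wording. Keep the purpose sentence on record and add a clarification, dated and marked as written after recruitment, that governs every conclusion:

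> This study is a cross-sectional comparison of corneal sensitivity and blink response between patients with type 2 diabetes of at least 10 years' known duration and mild to moderate PN, and younger non-diabetic subjects with no history of PN. Early detection of DPN, and separation of neuropathy from diabetes or age, are not tested.

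The cost is two sentences and a narrower claim. No new participants or procedures are needed.

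Optionally, report the ROC AUC with a 95% confidence interval. Label it post hoc and title it *mild to moderate DPN versus non-diabetic controls*, with a statement that it is confounded by diabetes and age. It uses only data described as collected, but it will be imprecise. By the Hanley-McNeil formula, an assumed AUC of 0.75 with 28 and 16 subjects has a standard error of 0.0733, so the interval is about ±1.96 × 0.0733 = ±0.14. The main fix does not depend on it.

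### The controls average 49.8 years, below the plan's own age limit of 50, and the only planned test is unadjusted for the 17-year age gap

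*Combined protocol and SAP*

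**What the plan says.** All of this is in the Study Protocol and Data Analysis sections of the combined document.

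- **Recruitment.** The sentence begins "Diabetes patients meeting the criteria were recruited from the Diabetes Clinics and non-diabetic" and continues "subjects from the general veteran population". The criteria are mentioned in connection with the diabetic patients; for controls only a source is given.
- **Groups.** The two groups are diabetic "with peripheral neuropathy and non-diabetic with no history of peripheral neuropathy". Being non-diabetic without such a history is the only condition stated expressly for controls.
- **Inclusion criteria.** Item 3 sets a minimum age of 50. Items 1, 2 and 5 (type 2 diabetes, its duration, neuropathy) can apply only to diabetic patients.
- **Exclusion criteria.** The list covers smoking, nerve-active medication, corneal disease or dry eye, and contact lenses ("8) History of wearing contacts"). It names no group.
- **Participants.** "The study included 28 patients with type 2 diabetes and peripheral neuropathy"; "The average age of the diabetes patients was 66.8 ± 1.9". The control description starts "The non-diabetic subjects (11 male and 5" and ends "female) were younger 49.8 ± 5.0".
- **Analysis.** Results are given as mean ± S.E.M. The groups are compared by Student t-test at p < 0.05. No matching, age restriction or covariate is mentioned.

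**The concern.** The age limit and the reported control mean do not fit together if the limit was meant for everyone. If it was meant for the diabetic patients alone, the groups entered under different age rules. On either reading the comparison contains controls of an age at which no eligible diabetic patient exists.

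The study's purpose is early detection of diabetic neuropathy from corneal function. If corneal sensitivity or blinking changes with age, a 17-year difference in mean age produces a group difference without any contribution from neuropathy, and the planned t-test has no means of separating the two. Age adjustment across the whole sample would not fully repair this, because below 50 a model could only extrapolate for the diabetic group.

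**Working it through.** The plan gives no sample-size or power figure to reproduce, and no individual ages. The check uses the published summaries.

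**Inputs.** Diabetic group: n = 28, age 66.8 ± 1.9. Controls: n = 11 + 5 = 16, age 49.8 ± 5.0. Limit: 50. ± is S.E.M. (Data Analysis).

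**1. Certain from the mean alone.** Before rounding, the control mean lies between 49.75 and 49.85. Sixteen values all at or above 50 cannot average less than 50, so at least one control is under 50, whatever ± means.

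**2. Spread.** SD = S.E.M. × √n. Controls: 5.0 × √16 = 20.0. Diabetic group: 1.9 × √28 = 10.05.

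**3. Lower bound without a shape assumption.** An S.E.M. that rounds to 5.0 is at least 4.95, so the sum of squared deviations is at least 16 × 15 × 4.95² = 5,881. Assume ages start at 18.
- Two controls under 50, upper age 95: the largest possible sum is 2 × 31.8² + 45.2² + 16.0² + 12 × 0.2² = 4,322, which is too small.
- Three under 50, upper age 95: the largest sum is 7,129, which is enough.
- Over assumed upper ages of 85 to 100 the minimum is three; over 70 to 80 it is four.

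**4. Likely number.** If ages are about normal, P(age < 50) = Φ((50 − 49.8)/20) = 0.504, or about 8 of 16.

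**5. Age gap.** 66.8 − 49.8 = 17.0 years. Standard error = √(1.9² + 5.0²) = 5.35; t = 17.0/5.35 = 3.18; Welch 95% CI 5.8 to 28.2.

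**6. Effect on the t-test.** The documents give no age effect, so a range is assumed: 0.2 to 0.4 SD of the outcome per decade, no disease effect, ages about normal with the means and SDs above.

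| Age effect | Rejection rate, all controls (two sets of runs) |
|---|---|
| Linear | 18-43% and 19-46% |
| Starting at 50 | 8-18% and 9-19% |

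The ends move by a few points with how the ages are drawn, so I quote them as roughly 15-45% and 8-22%. With controls limited to 50 or over, and still assuming S.E.M. and near-normal ages, rejection was 5-6%.

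**7. Price of restriction.** Ratio of standard errors = √(1/28 + 1/m) / √(1/28 + 1/16), where m is the number of controls kept and the denominator is 0.313. With m = 8: 0.401/0.313 = 1.28. With m = 12: 0.345/0.313 = 1.10. With m = 4: 0.535/0.313 = 1.71. These are before age adjustment.

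**The case against.** Four counter-arguments deserve weight.

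**Control eligibility.** A reader might infer that the exclusions were not applied to controls, so that smokers, lens wearers or people with dry eye diluted the contrast. The documents do not support that. The inference rests on one recruitment phrase, the exclusion list names no group, and no figure suggests that any control would have failed it. The plan is silent here. This objection stands in full.

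**Restriction alone may not close the gap.** A reader might infer that applying the limit of 50 to controls brings the groups level. For normal ages with SD 20, controls aged 50 or over average 49.8 + 20 × 0.399/0.496 = 65.9, leaving about 1 year. That depends on shape. With ages from 18 to 80 (assumed), between 4 and 12 controls can be under 50. If only 4 to 6 are, the older controls average about 58 to 64.5, leaving a gap of about 2 to 9 years. This stands, and is why the fix needs age adjustment as well.

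**± may not be S.E.M. for baseline figures.** HbA1c of 8.2 ± 0.3 read as S.E.M. gives SD = 0.3 × √28 = 1.59. With values between an assumed floor of 5% and the limit of 9.0%, the largest SD is about √(0.8 × 3.2) = 1.60, so that reading is strained. If the control figure of 5.0 were an SD, normal controls aged 50 or over would average about 54, leaving a gap of about 13 years, and restriction alone would still give about 10-23% false positives. The stated convention is S.E.M., but the doubt is fair. It does not touch the finding of at least one control under 50.

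**Unreadability.** A reader might infer that the corneal result cannot be read as a neuropathy effect at all. The figures show inflated false-positive rates under assumed age effects, which is less than that.

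**Conclusion.** The point holds. Without assumptions: the control mean is below the plan's age limit, at least one control has no eligible diabetic counterpart, the groups differ by 17.0 years on average, and the planned t-test does nothing about it. If ± is S.E.M. and ages start at 18, at least three or four of the 16 controls are affected; about half if ages are also roughly symmetric.

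The false-positive rates of roughly 15-45% (linear age effect) and 8-22% (effect from 50) rest on the assumed slope of 0.2 to 0.4 SD per decade, on near-normal ages and on S.E.M. They indicate scale and are not estimates for this study. Whether the exclusions covered controls is a secondary question of clarity and not a shown error.

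**What to change.** 1. For every corneal comparison, add an analysis limited to participants aged 50 or over in both groups, with group and age as terms in a linear model. Report the group difference and its 95% CI beside the all-subject t-test. Since enrolment is described in the past tense, label the analysis as added.
2. Attribute a difference to diabetic neuropathy only where this analysis supports it, for example where its 95% CI excludes zero, in line with the plan's 0.05 level. Otherwise describe the difference as confounded with age.
3. State how many controls are under 50, give the age range in each group, and say whether ± on the ages is S.E.M. or SD.
4. State whether the age limit and the exclusions applied to controls. The documents do not say that lens, smoking or medication histories were recorded for controls, so this may have to be answered as unknown.

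**Cost.** A few sentences and a re-run on ages already collected. The restricted analysis keeps about 8 controls if ages are roughly symmetric, plausibly 4 to 12. At 8 the standard error is about 28% larger before age adjustment, and the interval is correspondingly wider. The all-subject result remains in the report.

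### The lid-closure outcome has no resting reference, so a group difference in lid closure at rest would pass into the reported blinking response

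*Combined protocol and SAP*

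**What the plan says.** The Ophthalmic assessment section offers two tests as evaluations of corneal sensitivity: "Bonnet aesthesiometer examination and blinking response determination following application" of a saline drop. The drops are isotonic saline (308 mosmol/liter) and 5% sodium chloride (1710 mosmol/liter).

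- **First drop.** "Video was taken continuously at 30fps of each subject as an isotonic solution was" given, and the text goes on: "delivered to the left eye. The response was video recorded for 60 sec after a 10 sec delay".
- **Second drop.** "After a 15 min wash and rest period the procedure was repeated using a drop of Muro-128" solution. No randomised or alternated order is described. The left eye is named only for the first drop; that the second went to the same eye is inferred from the statement that the procedure was repeated.
- **Frames analysed.** They are taken every "10 seconds from each eye drop concentration epoch; therefore 15 images were analyzed" per subject and solution. No epoch before a drop is named.
- **Scaling.** Closure is expressed relative to the subject's "maximum visible eye surface area between the eyelids during that epoch".
- **Analysis.** The Data Analysis section gives one method: a Student t-test of control against diabetic subjects at the 0.05 level. It has no baseline, period or covariate term.

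**The concern.** A response to a stimulus is a change from the state before it. Here the measure is the level of lid closure after the drop, and nothing in the outcome or the analysis refers to the level before it. Dividing by the widest opening in the same epoch allows for the size of the eye opening. It does not allow for how much the subject closes or blinks when undisturbed.

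Equal resting behaviour cannot be presumed. The Study Protocol section reports mean ages of 66.8 ± 1.9 in 28 diabetic patients and 49.8 ± 5.0 in 16 non-diabetic subjects. At stake is the reading of the blink test: a difference in resting closure or spontaneous blinking would be reported as a difference in blinking response, and so as altered corneal sensitivity. The fixed order adds a second, narrower problem for any claim that the stronger solution itself changed closure.

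**Working it through.** The documents state no sample-size, power or SD figure for the lid outcome, so there is none to reproduce. The question is what the two recordings can identify.

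**1. What is estimable now.** Write r for resting closure, d for the effect of any drop, h for the extra effect of the hypertonic drop, p for order and c for carry-over. Assuming these add:

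- isotonic epoch: Y1 = r + d
- Muro-128 epoch: Y2 = r + d + h + p + c

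Two means carry five unknowns (rank 2 of 5). Only r + d and h + p + c can be estimated.

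**2. What the planned t-test compares.** With Δ for diabetic minus control:

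- isotonic: Δr + Δd
- Muro-128: Δr + Δd + Δh + Δp + Δc

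Δr enters both in full. If order and carry-over are the same in both groups, Δp = Δc = 0 and they cancel.

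**3. Example (assumed values).** Let resting closure be 20% and 15%, with a 10-point drop effect in both groups.

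- Post-drop: (20 + 10) − (15 + 10) = 5 points, all of it resting behaviour.
- Change from pre-drop: (30 − 20) − (25 − 15) = 0.
- Muro-128 minus isotonic, with common h, p and c: the difference is h + p + c in each group, so the groups differ by 0.

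**4. Size for the planned test.** Inputs: n = 28 and 16 (11 + 5), df = 42, α = 0.05 (two-sided assumed). The shift δ is in within-group SD units and is assumed. Noncentrality = δ / √(1/28 + 1/16) = δ / 0.313. With identical drop responses in both groups:

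| Resting difference δ (SD) | Noncentrality | Probability of p < 0.05 |
|---|---|---|
| 0 | 0 | 0.05 |
| 0.25 | 0.80 | 0.12 |
| 0.5 | 1.60 | 0.34 |
| 0.75 | 2.39 | 0.65 |
| 1.0 | 3.19 | 0.88 |

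**5. Comparability of the groups.** Age difference: 66.8 − 49.8 = 17.0 years. If the ± values are standard errors, as the Data Analysis section says of results, this is 17.0 / √(1.9² + 5.0²) = 17.0 / 5.35 = 3.2 standard errors.

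**6. A within-subject osmolarity claim.** No paired test is planned. If one were run with no true hypertonic effect and an assumed order shift of 0.5 SD of the paired difference, the noncentrality is 0.5√28 = 2.65 in the diabetic group and 0.5√16 = 2.0 in controls. The probability of p < 0.05 is then 0.72 and 0.47.

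**7. What pre-drop epochs add, order unchanged.** Let s be drift in the resting level and q an order or carry-over effect on the response itself. Then B1 = r, Y1 = r + d, B2 = r + s, Y2 = r + s + d + h + q.

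- Y1 − B1 = d
- B2 − B1 = s
- Y2 − B2 = d + h + q

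This is rank 4 of 5. Resting level and its drift are separated, but q stays tied to h.

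**8. Does pre-drop footage exist?** A 60 s window at one frame per 10 s gives 6 or 7 frames, and 70 s gives 7 or 8. Counting two eyes separately gives 12 to 16, and none of the counts from these windows is exactly 15. Fifteen successive frames would span 140 to 150 s. The recorded span is therefore unclear from the text.

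**The case against.** The strongest reply is that the only planned analysis is between groups and both groups follow the same sequence, so a common habituation, fatigue or carry-over effect drops out. That stands. A reader might infer from the fixed order that the diabetic-control comparison is invalid; the documents do not support this, because bias needs an order or carry-over effect that differs by group.

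Three further tempting readings go too far:

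- **That nothing was recorded before the drops.** The text says only that video ran continuously while the isotonic drop was given. Some earlier frames may exist. What can be said is that none is described or used.
- **That comparing the two drops within subject is no help.** It removes a stable resting difference and any common order effect (step 3). Only a group-specific order or carry-over effect survives.
- **That the assessment of corneal sensitivity rests on lid closure alone.** Cochet-Bonnet aesthesiometry is a separate measure.

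The design also has partial safeguards. The isotonic drop is some control for drop delivery, the interval between drops includes washing as well as rest, giving the stronger solution last plausibly limits carry-over, and the cameras "laterally, were used to observe both eyes simultaneously". The plan, however, uses none of these to estimate or test resting behaviour or recovery.

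Finally, the sizes above rest on assumed shifts and on effects that add, for an outcome scaled to each epoch's own maximum. They show what a resting difference would do, not that one exists.

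**Conclusion.** The point holds for the missing resting reference. A resting difference of any size passes in full into both single-drop comparisons. For assumed differences of 0.25 to 1.0 SD, it would produce a significant result with probability 0.12 to 0.88 when the groups respond identically to the drop. The reported 17-year age gap makes equal resting behaviour unsafe to assume, and the plan as written cannot check it.

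Order and carry-over are a lesser matter. They bias the planned test only if they differ by group, but even a common effect would confound a within-subject claim about osmolarity.

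This rests on reading the described epochs as the only ones analysed, on a two-sided test and on additive effects. It is a cheap improvement that should be made, not a finding that the comparison is invalid.

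**What to change.** **Where recording is still possible, or the existing video already covers it.** Record or extract an undisturbed epoch, for example 60 s, before each drop. Compare the groups on post-drop closure with that drop's pre-drop value as covariate, or on the change, and name one as primary in advance. Compare the two pre-drop epochs, within subject and by group, to check that resting lid behaviour had recovered after the 15 min interval. The order of solutions can stay as written. An order or carry-over effect on the response itself then remains inseparable from the hypertonic increment, so claims about osmolarity should stay limited.

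**Where no usable pre-drop frames exist.** The text is in the past tense, so this may be the case. Compare the groups on the within-subject Muro-128 minus isotonic difference, and state that a group-specific order or carry-over effect remains. This contrast addresses only the extra response to the stronger solution, because the effect common to both drops cancels. Describe the single-drop results as lid closure after the drop, not as corneal sensitivity.

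**Cost.** New recording takes 2 × 60 s, about two minutes of chair time per subject with cameras already in place, plus two more epochs to read. A change score adds some measurement noise, which covariate adjustment limits. The Muro-128 minus isotonic comparison needs no new data.

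### The only named analysis is an unadjusted t-test between non-randomised groups whose mean ages differ by 17.0 years, so a corneal or blink difference cannot be separated from age

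*Combined protocol and SAP*

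**What the plan says.** Groups were formed by disease status: diabetic "with peripheral neuropathy and non-diabetic with no history of peripheral neuropathy" (Study Protocol). The diabetic patients came from diabetes clinics, and the comparison group was "subjects from the general veteran population".

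The same section reports the ages: "The average age of the diabetes patients was 66.8 ± 1.9" for 28 patients, while the non-diabetic subjects (11 male, 5 "female) were younger 49.8 ± 5.0"). The document therefore notes the imbalance itself.

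The outcomes are in the Ophthalmic assessment section, in the text that begins "To evaluate cornea sensitivity each patient underwent a Cochet": an aesthesiometer examination and a blink response to two saline drops. Eyelid closure is expressed relative to each subject's "maximum visible eye surface area between the eyelids during that epoch".

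The Data Analysis section has three elements: results as mean and S.E.M., a control-versus-diabetic comparison ("subjects were conducted using Student t-test (Prism software; GraphPad, San Diego, CA"), and a 0.05 threshold. No covariate, matching, stratification or age restriction appears anywhere in the document.

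**The concern.** The stated purpose is a new approach to early detection of diabetic neuropathy. That requires reading a corneal or blink difference as a consequence of disease. If either outcome changes with age, the unadjusted difference in means contains 17.0 years of that change plus any disease effect, and the t-test cannot divide the two. A small p-value does not help, because the test addresses chance and not the imbalance. Scaling closure to a subject's own maximum eye opening removes differences in eye size; it does not remove an age effect on blinking. Followed as written, the plan could report an age difference as a disease difference.

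**Working it through.** The plan states no sample-size calculation, effect size or outcome SD, so there is no figure of its own to reproduce.

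**Inputs (Study Protocol).** Diabetic: n = 28, age 66.8 ± 1.9. Non-diabetic: n = 11 + 5 = 16, age 49.8 ± 5.0. Threshold 0.05 (Data Analysis), taken as two-sided.

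**Age gap.** 66.8 − 49.8 = 17.0 years.

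**Bias.** With an age effect that is linear and equal in both groups, expected spurious difference = slope per year × 17.0. The meaning of ± does not enter.

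**Age spread, ± as S.E.M.** (the only definition given). SDs are 1.9 × √28 = 10.05 and 5.0 × √16 = 20.0. Pooled SD = √[(27 × 10.05² + 15 × 20.0²)/42] = 14.42. Standardised age gap = 17.0/14.42 = 1.18.

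**Illustration with no disease effect.** The outcome is scaled to a within-group SD of 1, and r is an assumed pooled within-group correlation of outcome with age. Slope = r/14.42; expected difference = 17.0 × slope. The standard error of the difference is √(1/28 + 1/16) = 0.313. The rejection rate is from the noncentral t with 42 df and noncentrality difference/0.313.

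| Assumed r | Slope (SD per year) | Expected spurious difference (SD) | p < 0.05 |
|---|---|---|---|
| 0 | 0 | 0 | 5% |
| 0.1 | 0.007 | 0.12 | 7% |
| 0.2 | 0.014 | 0.24 | 11% |
| 0.3 | 0.021 | 0.35 | 20% |
| 0.5 | 0.035 | 0.59 | 45% |

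Simulation with normal ages and the separate group SDs (20,000 runs per row) gives 5.2, 6.5, 11.3, 20.1 and 45.3%. In the same runs a linear model on group and age rejects in 4.8 to 5.3%.

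**Same slopes, ± as SD.** Pooled age SD = √[(27 × 1.9² + 15 × 5.0²)/42] = 3.35. Keep the slope and residual SD of each row, so that outcome SD = √[(1 − r²) + (slope × 3.35)²]. For the last three rows this is 0.981, 0.956 and 0.874. The standardised differences become 0.24, 0.37 and 0.67, and the rejection rates 12, 21 and 56%. The reading of ± changes these little except at the steepest slope.

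**What ± does change: the precision of adjustment.** Variance inflation for the group term = 1 + D²/[42 × (1/28 + 1/16)], where D is the standardised age gap.
- S.E.M. reading: D = 1.18, inflation 1.34, standard error × √1.34 = 1.16.
- SD reading: D = 17.0/3.354 = 5.07, inflation 7.23, standard error × 2.69.

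**Is ± certain?** No. The patients' "hemoglobin A_{1C} 8.2 ± 0.3", read as S.E.M., implies an SD of 0.3 × √28 = 1.59, which fits poorly with the inclusion limit of HbA1c below 9.0%. Against that, an age SD of 1.9 among 28 people would be narrow. The authors need to say which it is.

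**The case against.** The strongest reply is that nothing in the document says corneal sensitivity or blink response varies with age. That stands. Every non-null row in the table rests on an assumed slope, and at slope zero there is no bias. What remains is that the named analysis cannot tell age from disease, and this does not depend on any particular slope.

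A second reply is that S.E.M. is the only definition of ± given, and that the HbA1c figure is a separate reporting puzzle which says little about the ages. That is fair, and is why the illustration uses S.E.M. The SD reading matters only for whether adjustment is workable.

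Three stronger inferences are tempting and should be resisted.
- A reader might infer that an observed difference is an age effect. The documents show only that the analysis cannot exclude it.
- A reader might infer that, if ± is SD, false positives become near certain (88% at r = 0.2, close to 100% at r = 0.3). Holding r fixed across the two readings assumes an age slope 14.42/3.354 = 4.3 times steeper on the SD reading. At equal slopes the rates are close, as shown above.
- A reader might infer that a difference above about 0.6 SD is safe from this explanation, because the largest tabulated bias is 0.59 SD. That figure is an expectation and not a ceiling. With age alone at r = 0.5, the 95% range of observed differences reaches about 0.59 + 1.96 × 0.313 = 1.20 SD, and about 25% of studies exceed 0.8 SD.

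**Conclusion.** The point holds. One unadjusted t-test between non-randomised groups from different sources, 17.0 years apart in mean age, cannot support attribution of a difference to disease. The size of the problem is unknown because the documents give no age slope. Over the assumed slopes of 0 to 0.035 outcome SD per year, the expected spurious difference runs from 0 to 0.59 SD and the false-positive rate from 5 to 45%. This assumes no disease effect, linearity in age and ± read as S.E.M. The meaning of ± governs age overlap and the precision of an adjusted estimate; the size of the confounding turns mainly on the unknown slope. The point should be fixed before the results are interpreted.

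**What to change.** 1. State whether ± for age is SD or S.E.M. Report each group's age distribution and how many subjects lie in the shared age range.
2. Make the main comparison of the continuous corneal and blink outcomes a linear model on group and individual age. Report the adjusted difference with its 95% CI. Label it a reanalysis, because the text is written after the study was done. Keep the unadjusted t-test as descriptive.
3. Add a sensitivity analysis restricted to the shared age range, stating how many controls remain. The listed entry age is 50 or over and the control mean is 49.8, so at least some controls are under 50. If every diabetic patient met that criterion, those controls drop out.
4. If the ages barely overlap, report that the group difference cannot be separated from age, and do not attribute it to diabetes or neuropathy.

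**Cost.** No new assessments are needed, but individual ages must be linked to outcomes; the document shows only group summaries. On the S.E.M. reading, if age turns out to be irrelevant, the standard error of the group effect is about 16% larger and power for a true 1-SD difference falls from 88% to about 76–77%. On the SD reading the standard error is about 2.7 times larger and the adjusted estimate is mostly extrapolation, so step 4 would apply.
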